#### **4.4 End of Study Definition**

A participant is considered to have completed the study if he or she has completed all phases of the study including the last visit or the last scheduled procedure shown in [Section 1.3 Schedule of Assessments](#).

The end of the study is defined as completion of the last visit or procedure shown in the Schedule of Assessments in the trial overall.

## **5 STUDY POPULATION**

### **5.1 Inclusion Criteria**

To be eligible to participate in this study, an individual must meet all of the following criteria:

- 1) Provision of signed and dated informed consent form (ICF)
- 2) Stated willingness to comply with all study procedures and availability for the duration of the study
- 3) Male or female, aged  $\geq 18$  years
- 4) Diagnosed with active UC for at least 3 months prior to screening
- 5) Total Mayo score  $\geq 5$  and Endoscopic sub-score  $\geq 1$
- 6) Stable dosing regimens of oral drugs (if currently administered) as follows: 5-ASA or sulfasalazine at a stable dose for at least 4 weeks, purine analogues (azathioprine, mercaptopurine, thiopurines) or immunosuppressants (methotrexate, cyclosporine) at a stable dose for at least 12 weeks, and low-dose oral corticosteroid (up to 20 mg prednisone/day or equivalent) for at least 4 weeks prior to the first dose of study treatment. Doses of oral drugs must remain stable until the end of study treatment (with possible exception for tapering steroid dose after 8 weeks)
- 7) For females of reproductive potential: use of highly effective contraception for at least 1 month prior to screening and agreement to use such a method during study participation and for an additional 3 months after the last dose
- 8) For males of reproductive potential: use of condoms or other methods to ensure effective contraception with partner during study participation and for an additional 3 months after the last dose

### **5.2 Exclusion Criteria**

Individuals who meet any of the following criteria will be excluded from this study:

- 1) Use of anti-TNF- $\alpha$  biologics, any other biologics, or tofacitinib for treatment of UC within 60 days prior to randomization
- 2) Any rectal therapy for treatment of UC or intravenous corticosteroids within 2 weeks prior to randomization
- 3) Presence of Crohn's disease, indeterminate colitis, ischemic colitis, fulminant colitis, ulcerative proctitis, or toxic mega-colon
- 4) Previous extensive colonic resection (subtotal or total colectomy)
- 5) Ileostomy, colostomy, or known fixed symptomatic stenosis of the intestine
- 6) Evidence of treatment for *Clostridium difficile* infection or other pathogenic bowel infection within 60 days or for another intestinal pathogen within 30 days prior to randomization
- 7) Active infection with the HIV or Hepatitis B or C viruses

- 8) Clinically significant active extra-intestinal infection (e.g., pneumonia, pyelonephritis)
- 9) Clinically significant abnormal vital signs, physical examination or 12-lead electrocardiogram (ECG) at screening or baseline
- 10) Clinically significant abnormal results of liver function tests (ALT/AST, bilirubin and alkaline phosphatase) > 2X the upper limit of normal (ULN) at screening
- 11) Other clinically significant abnormal laboratory results at screening in the investigator's opinion
- 12) History of any clinically significant medical condition that, in the investigator's opinion, would preclude participation in the study
- 13) Pregnancy or lactation
- 14) Treatment with another investigational drug or other intervention within 30 days prior to screening

### **5.3 Lifestyle Considerations**

No new non-pharmacological therapies should be started during the study period. In addition, no elective surgery should be scheduled during the study period. Patients should avoid smoking cessation during the study and should maintain existing habits, such as exercise levels and dietary habits throughout the study. Contraceptive measures for both males and females of childbearing potential should be documented in the source documents.

### **5.4 Screen Failures**

Screen failures are defined as participants who consent to participate in the clinical trial but are not subsequently randomized in the study. A minimal set of screen failure information is required to ensure transparent reporting of screen failure participants, to meet the Consolidated Standards of Reporting Trials (CONSORT) publishing requirements and to respond to queries from regulatory authorities. Minimal screening failure information includes demography, screen failure details, eligibility criteria, and any SAE.

### **5.5 Strategies for Recruitment and Retention**

The study plans to enroll up to 48 adult patients (aged  $\geq 18$  years) with active UC in the United States and South Korea.

## 6 STUDY INTERVENTION

### 6.1 Study Drug Administration

#### 6.1.1 Study Drug Description

BBT-401-1S is the monosodium salt of BBT-401, an N-terminal lipidated 4aa peptide that targets Pellino E3 ubiquitin protein ligase 1 (Pellino-1) which leads to suppression of NF- $\kappa$ B-mediated inflammatory signals ([Choi et al, 2006](#); [Jiang et al, 2003](#); [Lee et al, 2015](#)).

#### 6.1.2 Dosing and Administration

BBT-401-1S or placebo will be administered orally in capsule form. Study medication will be self-administered by the subject. Patients should be advised not to crush, break, chew, or dissolve the capsules. On days with scheduled study visits, patients should not take their dose of study medication at home in order to complete pre-dose study procedures including PK and safety lab. Patients will be instructed to fast for up to eight hours before their scheduled study visits.

Dosing will be determined for 3 cohorts conducted sequentially, starting with the first cohort that will receive BBT-401-1S 400 mg once daily.

Patients will receive a daily oral dose of BBT-401-1S or placebo for the 16 weeks. While patients who are assigned to Active Group will receive BBT-401-1S for the first 12 weeks and then placebo for the last 4 weeks, patients who are assigned to Placebo Group will receive placebo for the first 8 weeks and then BBT-401-1S for last 8 weeks.

Efficacy, safety, and PK data of the first cohort will be used to select the dose of the subsequent cohort. After 75% of patients of the current dose level cohort complete Visit 4 (Week 8), sponsor will review all pertinent data and decide dose level of next cohort. Dose level can be increased within 2-fold of previous dose level. A dose level may be repeated or added based on results of the previous cohort(s). The highest dose is not to exceed 1,600 mg daily.

Based on nonclinical toxicology studies, the safety margin of BBT-401-1S in humans is expected to be high. BBT-401-1S showed no noteworthy findings of drug related AEs at SAD up to 1,600 mg per person and at MAD 400, 800, and 1,600 mg daily per person in the Phase 1 clinical trial in healthy subjects. However, in the absence of an adequate clinical safety database in active UC patients, every investigator should be aware that BBT-401-1S has the potential to cause certain adverse effects by virtue of its pharmacological action and based on clinical experience with compounds of similar pharmacological effect. Please refer to the current IB for additional information regarding expected and anticipated adverse reactions. Please refer to [Sections 6.6](#) of this protocol for additional information regarding reasons for discontinuation of study intervention and participant discontinuation/withdrawal from the study.

## 6.2 Preparation/Handling/Storage/Accountability

### 6.2.1 Acquisition and accountability

The investigator will maintain accurate records of the receipt of all study medications. In addition, accurate records will be kept regarding when and how much study medication is dispensed and used by each patient in the study. Reasons for deviation from the expected dispensing regimen must also be recorded. Study medication will be reconciled by the site. The investigator agrees to provide sufficient access to study medication as required for the reconciliation process to be completed in a timely fashion.

### 6.2.2 Formulation, Appearance, Packaging, and Labeling

The oral drug product, BBT-401-1S capsules for use in the clinic will be administered as a delayed-release (DR) capsule containing 200 mg of BBT-401-1S, the monosodium salt of an N-terminal lipidated tetrapeptide. The formulation has been manufactured so as to selectively fuse particles of an Eudragit®, pH-dependent enteric polymer, with adjacent particles of drug substance and HPMC to form a loose matrix powder. This powder is then blended with magnesium stearate and filled into white, opaque HPMC capsules to provide the labelled active strength.

The BBT-401-1S placebo capsules are intended to mimic the appearance of the active drug product, BBT-401-1S capsules, 200 mg. The content of the BBT-401-1S placebo capsules is a blend mixture of the same quantity of excipients as present in the drug product with the active ingredient replaced by microcrystalline cellulose. BBT-401-1S placebo capsules are filled to the same nominal weight as the drug product and are used as per the clinic dosing regimen.

BBT-401-1S 200 mg or placebo capsules will be provided in HDPE bottles of 32 capsules, sealed with a child-resistant closure. Each bottle of the test products (BBT-401-1S Capsules, 200 mg or Placebo) will be labeled with the following sample labeling:

Protocol Number: BBT401-UC-US02	IP Code: BBTXXXX
BBT-401-1S Capsules (200 mg or Placebo)	Quantity: 32 capsules
Lot: L334-01055BOT32/L334-01055ABOT32/L334-01056BOT32	Mfg Date: Sept-2018
For oral administration as directed in the study protocol.	
Store between 59-86°F (15-30°C) and ≤ 60% RH. Protect from exposure to high humidity. Protect from light. Keep out of reach of children.	
Caution: New Drug – Limited by United States law to investigational use.	
Manufactured by Corealis Pharma Inc., [name]	
Sponsor: Bridge Biotherapeutics Inc.	
US Representative: KCRN Research, [name], [contact]	

### 6.2.3 Product Storage and Stability

BBT-401-1S capsules will be stored at controlled room temperature (limited excursions permitted between 59°F and 86°F, 15-30 °C) and  $\leq$  60% RH. Protect from exposure to high humidity. The bottle should be tightly sealed after use.

### 6.3 Measures to Minimize Bias: Randomization and Blinding

A total of 16 subjects in each of the 3 dosing cohorts will be randomized to either active or placebo group in a 3:1 ratio (12 active and 4 placebo) using the electronic data capture (EDC) system.

The randomization code will be generated by a unblinded statistician who is not involved with the study. The Sponsor, investigators, patients, and CRO and other relevant personnel involved with the conduct of the study, with the exception of clinical supply staff and the unblinded statistician, will be blinded to the identity of study medication.

For the 1st or 2nd cohort, if the 12th patient (75%) completes Visit 4 (Week 8), the CRO data management (DM) team confirm all clinical data of the 12 patients have no issue and then obtain the written consent from the Sponsor to breaking the code. Per the request of the CRO DM team, the randomization codes of the 12 patients will be opened via the unblinded statistician and notified to the Sponsor for the analysis to determine the next dose. After confirming all clinical data of remaining 4 patients for the 1st or 2nd cohort, the randomization codes will be subsequently opened to the sponsor through the same procedures stated above.

After the last patient of last cohort completes the SFU, the CRO DM team confirm the whole clinical database has no issue and then request the database lock to the Sponsor. Per the Sponsor's approval on the database lock, the randomization code of all patients will be opened via the unblinded statistician and notified to the CRO for the statistical analysis.

Breaking of the randomization code without Company's permission is expressly forbidden except in the event of a medical emergency where the identity of the study medication must be known in order to properly treat the patient. In the event of a medical emergency, it is requested that the investigator make every effort to contact the study monitor or designee prior to breaking the code.

If the blind is broken due to the medical emergency, the subject must be early terminated; a written explanation must be prepared immediately.

### 6.4 Treatment Compliance

Treatment compliance with the study drugs will be documented by drug dispensing procedures, including a subject diary, on Visits 2–5 and by drug return and compliance assessments conducted on Visits 3–6 and/or Early Termination visit.

The investigator will manage the treatment compliance to be maintained between 80% and 120%. If the subject's drug compliance is deviated from the allowed treatment compliance at a scheduled visit, the investigator should explain the importance of drug compliance to the subject and re-instruct the dosing methods to the patient for appropriate administration of next doses.

## **6.5 Concomitant Therapy**

Concomitant therapy with the following oral drugs is allowed during the study, provided that the dosing regimen has been stable for the specified durations as assessed at screening:

- 5-ASA or sulfasalazine at a stable dose for at least 4 weeks prior to the first dose of study treatment
- Purine analogues (azathioprine, mercaptopurine, thiopurines) or immunosuppressants (methotrexate, cyclosporine) at a stable dose for at least 12 weeks prior to the first dose of study treatment
- Low-dose oral corticosteroid (up to 20 mg prednisone/day or equivalent) at a stable dose for at least 4 weeks prior to the first dose of study treatment

Doses of oral drugs must remain stable until the end of study treatment (with a possible exception for tapering the steroid dose after 8 weeks).

Concomitant therapy with anti-TNF- $\alpha$  biologics, any other biologics, or tofacitinib for treatment of UC within 60 days prior to randomization is not allowed, and individuals receiving such therapy will not be permitted to enroll in the study. Given the effects of anti-TNF- $\alpha$  biologics, other biologics, and tofacitinib on the inflammatory process, there is reasonable potential for interactions and/or confounding effects on the study endpoints.

Concomitant therapy with intravenous corticosteroids or any rectal administration therapy for treatment of UC within 2 weeks prior to randomization is not allowed, and individuals receiving such therapy will not be permitted to enroll in the study.

Assessments of concomitant therapy will be conducted at Visits 3–7.

## **6.6 Removal of Patients from the Trial or Study Drug**

The study may be terminated early if, in the opinion of the Sponsor, investigator, or IRB upon review of key safety data, an unacceptable risk to the safety and welfare of patients is posed by the continuation of the study.

Patients will be free to withdraw from the study at any time if so desired. A patient may be withdrawn from the study for any of the following reasons (including but not limited to):

- Withdrawal of consent - Any patient may withdraw his/her consent from the study at any time. The investigator should make a reasonable attempt to document the specific reason why consent was withdrawn.
- Deviation/noncompliance with the protocol or study drug
- AE
- Lost to follow-up

#### 6.6.1 Handling of Withdrawals

Although a patient is not obliged to give his/her reason for withdrawing prematurely, the investigator will make a reasonable effort to obtain the reason while fully respecting the patient's rights. If there is a medical reason for withdrawal, the patient will remain under the supervision of the study physician until in satisfactory health. Reasonable efforts will be made to contact a patient who fails to attend any follow-up appointments, in order to ensure that he/she is in satisfactory health.

If a patient is prematurely withdrawn or discontinues from this study, every attempt will be made to follow the early termination (ET) visit procedures described in [Section 7.4](#).

#### 6.6.2 Replacements

Patients who terminate early from the study will not be replaced.

## **7 STUDY ACTIVITIES**

### **7.1 Screening Visit (Day -28 to -1)**

Patient's eligibility for the study will be evaluated during this period based on medical history, physical examination, including flexible proctosigmoidoscopy or colonoscopy where indicated, laboratory values and additional tests.

Patients will be screened within 28 days prior to baseline and administration of study medication to confirm that they meet the entrance criteria for the study. The study investigator or appropriate delegate at the site will discuss with each patient the nature of the study, its requirements, risks and benefits. Written informed consent must be obtained prior to performing any protocol-specific procedures, including washout of prohibited medications.

In addition to obtaining informed consent, the following procedures will be performed:

- Collection of demographic information
- Completion of medical history (including prior medication, history of alcohol and drug use, smoking status and weekly alcohol consumption)
- Vital signs (including temperature)
- Physical examination (including weight and height)
- 12-lead ECG
- Mayo score (stool frequency, rectal bleeding, endoscopic findings [flexible proctosigmoidoscopy/colonoscopy], physician's global assessment)
- Review of inclusion/exclusion criteria
- Blood sampling for clinical lab tests (serum chemistry, hematology, pregnancy, and CRP)
- Endoscopy which must be evaluated by a central reader to confirm the endoscopic sub-score for the eligibility.
- Biopsy sampling for histologic assessment and tissue concentration during the endoscopy.
- UCEIS
- Distribution of a fecal sample collection container for V2 (baseline) sample

### **7.2 Treatment Period**

#### **7.2.1 Visit 2 (Baseline, Week 0/Day 1)**

Visit 2 will occur within 28 days after Visit 1. In this visit, the eligibility of patients will be confirmed and eligible patients will be randomized to either active or placebo group for 16-week treatments. The following procedures will be performed during Visit 2:

- Confirmation of fecal samples
- Confirmation of medical history
- Vital signs (including temperature)

- Physical examination (including weight), which is waived if the screening visit is conducted within 10 days prior to Visit 2
- 12-lead ECG, which is waived if the screening visit is conducted within 10 days prior to Visit 2
- Confirmation of inclusion/exclusion criteria
- Randomization
- Mayo score (stool frequency, rectal bleeding, physician's global assessment)
- SIBDQ
- Blood sampling for clinical lab tests (serum chemistry, hematology, pregnancy, and CRP), which is waived if the screening visit is conducted within 10 days prior to Visit 2
- Blood sampling for pharmacokinetics: pre-dose, 3 and 6 hours post-dose
- Administration of study drug
- Record of AEs and concomitant medications
- Distribution of a fecal sample collection container for V3 (Week 4) sample
- Distribution of study drugs and subject diary

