### 1.3 Schedule of Assessments

	Screening	Treatment Period						SFU
	V1	V2	V3	V4	V5	V6	ET	
Visit Number	Up to W-4	Baseline	W4	W8	W12	W16	N/A	W2 from LD
Visit Period	N/A	Within 28 days from V1	±3 days	±3 days	±3 days	±3 days	N/A	+ 7 days from LD
Visit Window								
Informed Consent	X							
Demographic Information	X							
Medical/medication History	X	X						
Inclusion/exclusion Criteria	X	X						
Vital Signs	X	X	X	X	X	X	X	X
Physical Examination	X	X a	X	X	X	X	X	
12-lead ECG	X	X a	X	X	X	X	X	
Clinical Lab Tests and Serum Biomarker b	X	X a	X	X	X	X	X	X
Endoscopy (biopsy)	X			X			X c	
Randomization		X						
Mayo Score	X	X	X	X	X	X	X	
Ulcerative Colitis Endoscopic Index of Severity	X			X			X c	
Short Inflammatory Bowel Disease Questionnaire		X	X	X	X	X	X	
Fecal Biomarker d		X	X	X	X	X	X	
Plasma Pharmacokinetics e		X	X	X				
Tissue Concentration f	X			X			X c	
Drug Dispensing (with subject diary)		X	X	X	X			
Drug Return and Compliance			X	X	X	X	X	
AE and Concomitant Medication		X	X	X	X	X g	X g	X

AE = adverse event; ECG = electrocardiogram; SFU = Safety Follow-Up; V = Visit; W = Week; ET = Early Termination; LD = Last Dose

a Waived if the screening visit is conducted within 10 days prior to Visit 2 (Baseline).

b Serum chemistry, hematology, coagulation test, HIV and hepatitis screens, serum hCG (women with childbearing potential only), and serum CRP (not measured at SFU).

c Only if early termination occurs before Visit 4 (W8).

d Fecal calprotectin and fecal lactoferrin. A collection container will be dispensed to patients on the previous visit.

e Visit 2 (Baseline) and Visit 3 (W4): pre-dose and 3 and 6 hours post-dose; Visit 4 (W8): pre-dose only.

f During the endoscopy (flexible proctosigmoidoscopy/colonoscopy) for biopsy.

g Reviewing any changes in smoking habits of subject during the study period.

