#### 8.2.4.1 Laboratory Parameters

Clinical safety laboratory tests will be conducted as outlined in the Schedule of Assessments, and should be completed pre-dose. Laboratory tests will include the following:

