#### 8.2.4.2 Additional Tests

- Serum hCG will be performed at every visit for women with childbearing only.
- Serum FSH test can be performed to confirm postmenopausal status at screening only.
- Human immunodeficiency virus (HIV), hepatitis B (HBsAg), hepatitis C virus (RIBA 2 or 3), and VZV IgG antibody will be performed at screening only.

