### 8.2.4.3 Sample Collection, Storage, and Shipping

Blood samples for hematology, coagulation parameters, serum chemistry, HIV and hepatitis screens, serum hCG (women with childbearing potential only), and serum CRP will be collected according to the laboratory manual provided by the CRO and according to the Schedule of Assessments and descriptions of visits.

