#### 8.5.7 Reporting of Pregnancy

Serum pregnancy testing will be conducted for all female patients with child-bearing potential at screening and all treatment visits. If a female patient becomes pregnant during clinical study, the investigator should prepare and submit an initial pregnancy report to the Sponsor within 24 hours of becoming aware of the pregnancy. The investigator should follow up and document all progresses and results of pregnancy, even if the patient withdraws consent or terminate the clinical study. In addition, the investigator should prepare and submit the pregnancy outcome report within 24 hours of becoming aware of all results of pregnancy.

Pregnancy itself is not considered as an AE if the pregnancy is not related to the investigational product.

All SAEs that occur during pregnancy will be recorded in an SAE report and the reporting will be performed according to the SAE reporting procedures.

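### The 10-day laboratory waiver at Visit 2 covers a serum pregnancy test that two other sections require there, so a woman can be randomized and dosed with no Day 1 test

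*Protocol*

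**What the plan says.** Two sets of statements in the protocol give different answers for Visit 2.

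**Test waived.** Section 7.2.1 lists "Blood sampling for clinical lab tests (serum chemistry, hematology, pregnancy, and CRP), which is waived if the screening visit is conducted within 10 days" of Visit 2, so pregnancy testing is named inside the draw that may be skipped. The Schedule of Assessments (Section 1.3) says the same through two footnotes. Footnote a, on the Visit 2 laboratory cell, reads "Waived if the screening visit is conducted within 10 days prior to Visit 2 (Baseline", and footnote b gives the content of that row as "Serum chemistry, hematology, coagulation test, HIV and hepatitis screens, serum hCG (women with childbearing potential only), and serum CRP (not measured at SFU". SAP Section 3.1, Table 1 repeats the waiver.

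**Test required.** Section 8.2.4.2 states: "Serum hCG will be performed at every visit for women with childbearing only". Section 8.5.7 states: "Serum pregnancy testing will be conducted for all female patients with child-bearing potential at screening and all treatment visits". Neither mentions a waiver.

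**Where sites are told to look.** Section 8.2.4.1 says "Clinical safety laboratory tests will be conducted as outlined in the Schedule of Assessments, and should be completed pre-dose". Section 8.2.4.3 says samples, serum hCG among them, "will be collected according to the laboratory manual provided by the CRO and according to the Schedule of Assessments and descriptions of visits".

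Exclusion criterion 13 in Section 5.2 is "Pregnancy or lactation", and Section 7.2.1 has eligibility confirmed at Visit 2. No other Day 1 pregnancy test, such as a urine test, is specified.

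**The concern.** Visit 2 falls under Section 7.2 (Treatment Period) and includes both randomization and the first dose. A site that uses the waiver as written omits a test that Sections 8.2.4.2 and 8.5.7 demand. Since Section 10.11 counts any noncompliance with the protocol as a deviation, that site is in deviation while following the visit description. No rule says which text takes precedence.

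The practical stake is the check at first exposure, the one point where a positive result prevents dosing rather than stopping it. A pregnancy that becomes detectable between screening and Visit 2 would, under the waiver, not meet a scheduled test until Week 4, after dosing has begun. Section 8.5.2 makes pregnancy exposure reportable and requires the drug to be stopped at once when pregnancy is confirmed. The waiver also makes the Day 1 test depend on scheduling: women screened 11 to 28 days before Visit 2 are tested that day, and women screened 1 to 10 days before need not be.

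**Working it through.** The plan states no figure to reproduce. The check is a reading of the sections against each other, followed by interval arithmetic.

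**Does the waiver reach hCG?** Yes. The schedule footnotes alone would be weaker evidence, because the row in footnote b also contains HIV and hepatitis screens that are not repeated after screening. But Section 7.2.1 names pregnancy explicitly in the waived draw.

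**Do the other two sections cover Visit 2?** Yes. Section 8.2.4.2 covers every visit. Section 8.5.7 covers screening plus all treatment visits, and Visit 2 is a treatment visit by its place in Section 7.2.

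**Is Section 8.2.4.2 only a general remark?** No. It sets timing test by test, and it is the text that limits the HIV and hepatitis tests, which share the hCG row, to screening. It has to be read as operative for those tests, so it is hard to treat it as non-operative for hCG.

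**Inputs for the intervals**

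- Waiver limit: screening up to 10 days before Visit 2 (Sections 1.3 and 7.2.1).
- First dose: at Visit 2, taken as day 0 (Section 7.2.1).
- Week 4 visit: 28 ± 3 days from first dose (Section 7.2.2).
- Week 8 visit: 56 ± 3 days from first dose (Section 7.2.3).

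**Last pre-dose test to the Week 4 test**

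- With a Day 1 test: 28 − 3 = 25 to 28 + 3 = 31 days.
- Waived, with screening 10 days before: 10 + 25 = 35 to 10 + 31 = 41 days.
- Maximum added by the waiver: 41 − 31 = 10 days.

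**Comparison with later visits**

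- Longest Week 4 to Week 8 interval: (56 + 3) − (28 − 3) = 59 − 25 = 34 days. Later treatment visits have the same 4-week spacing and ±3-day windows, so the same maximum applies.
- Excess of the waived interval: 41 − 34 = 7 days.

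The waiver therefore creates the longest interval between scheduled pregnancy tests in the study. The documents do not give the number of women it would affect.

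**The case against.** The strongest reply is that the waiver is the more specific rule. It names pregnancy, it matches the schedule, and Sections 8.2.4.1 and 8.2.4.3 point to it. On that view the sponsor chose to accept a screening test up to 10 days old, two sentences elsewhere were left unadjusted, and adding an exception to them would be an equally valid repair. This does not remove the conflict. Sections 8.2.4.2 and 8.5.7 are the ones written for pregnancy testing, and even on this reading they need correcting. Editing them instead would make the text consistent but leave the Day 1 gap.

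The second reply concerns the comparison group. Section 7.2.1 does not require any Day 1 result to be known before dosing, and Section 8.2.4.1 could be met by drawing blood pre-dose. If results are not same-day, a woman screened 28 days earlier is dosed on an older known result than a waived woman. This point stands, and it is why exempting hCG from the waiver is not enough on its own.

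The third reply is that the 41 days is a worst case. That is correct: up to 10 of those days precede any drug, and time on drug before the Week 4 test is at most 31 days either way. A pregnancy may also come to light outside scheduled tests.

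The mitigation is real too. Highly effective contraception is required from at least 1 month before screening (Section 5.1), and Phase 1 plasma values were all below quantification (Section 4.3). That Phase 1 evidence comes from healthy subjects with 7 days of multiple dosing, while Section 6.1.2 acknowledges the lack of an adequate safety database in active UC. No endpoint, analysis set or dose decision is affected.

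**Conclusion.** The concern holds. The waiver contradicts Sections 8.2.4.2 and 8.5.7, and a site directed to the schedule and visit descriptions will probably follow the waiver. Women screened within 10 days of Visit 2 can then be randomized and dosed without a Day 1 pregnancy test, on a serum result up to 10 days old.

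The waiver adds at most 10 days: 41 instead of 31 from the last pre-dose test to Week 4, and 7 more than the 34 days allowed between consecutive later treatment visits. These are maxima, assuming screening exactly 10 days before Visit 2 and Week 4 at the late end of its window.

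Confidence is high in the contradiction and the arithmetic. The expected harm is limited and cannot be quantified from the documents. The point should be corrected because it concerns a participant-safety check at first exposure and the remedy is small.

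**What to change.** - In Section 7.2.1, footnote a of Section 1.3 and the matching note of SAP Table 1, add: the waiver does not apply to serum hCG. The protocol edits carry the substance; the SAP edit keeps its copy of the schedule consistent.
- In Section 7.2.1, add that for women of childbearing potential a negative pregnancy result must be available before the first dose at Visit 2.
- Leave the waiver for chemistry, hematology, coagulation and CRP unchanged. Sections 8.2.4.2 and 8.5.7 then stand as written.

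The cost is one clause in three places, one sentence, and one already-listed assay for women screened within 10 days. A pre-dose PK sample is already drawn at Visit 2, so the hCG tube can be taken with it.

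The negative-result sentence reaches all women of childbearing potential, not only those under the waiver. Because Visit 2 also includes dosing and PK samples 3 and 6 hours later, a result that is not same-day could delay or split the visit. Laboratory turnaround is not stated in the documents and should be confirmed before the wording is finalized.
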